6.4.6 Adverse Events Reporting Timeline

All SUAE associated with the use of the study drug (ie in the setting of MetHb $> 10\%$ or discovered to be drug associated after unblinding by the safety monitor and considered potentially resulting from the study drug by the DSMB) will be reported to the IRB within 24 hours of discovery of the incident with subsequent follow-up submission of a detailed written report.

The FDA will be notified by telephone or facsimile transmission of a human SUAE no later than 7 calendar days after receiving the respective human adverse event information, followed by the

subsequent submission of a written IND Safety Report.

Serious and unexpected adverse events associated with the use of the study drug or procedures will be reported to the IRB with subsequent follow-up submission of a detailed written report in accordance with the respective policies and procedures of the IRB. Written IND Safety Reports will be submitted to the FDA as soon as possible and, in no event, later than 15 calendar days following the investigator-sponsor's receipt of the respective adverse event information.

A summary report of the findings will be prepared and submitted to the regulatory agencies.

6.4.7 Withdrawal of Subjects and Stopping Criteria:

Subjects withdrawn from the study due to concern for SAE will be followed for all clinical outcomes but no further lab or imaging data will be collected. These subjects will not be replaced within the study. Subjects will not be withdrawn after enrollment except if requested by the subject or surrogate after notification. In this event all data and specimens required for study outcomes obtained up to that time and clinical outcomes to DC will be retained.

Discontinuation of the Clinical Trial:

This study can be stopped only by the DSMB. In such a case we will complete collection of clinical outcomes in all enrolled subjects (up to 90 d after OHCA). Subjects will not be notified of early study termination.

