The following data elements will be collected during the course of the study at the times indicated. Data elements marked with an asterisk indicate variables or outcomes essential for conduct of the study and analysis of efficacy and/or safety. These data elements should be obtained in all subjects with no missing data expected. In addition to these data elements, we are collecting a large amount of secondary data intended for use in mechanistic studies and hypothesis generation. In many cases, these data elements WILL NOT be able to be collected in all subjects. Such missing data will be handled as designated within an a priori statistical analysis plan but the presence of missing data will in no way impede our ability to meet the objectives of this phase 2 RCT.

BASELINE DATA

- *Date of OHCA
- *Time of OHCA (If not available we will use Time of ROSC after subtracting estimated no flow and CPR time based on transfer records/physician report)
- Witnessed
- Bystander CPR
- EMS Call Date
- EMS Call Time
- EMS Arrival Date
- EMS Arrival Time
- No flow time
- CPR (low flow) time
- Presenting rhythm
- *Date and Time of ROSC (If not available we will use ED admission date/time from referring hospital record. If unavailable, stat medevac call date/time minus 30 mins. If unavailable, time of arrival minus 15 min)
- PCAS ID
- *Last name
- *First name
- *Date of Birth
- *Medical record number
- Marital status
- Race/Ethnicity
- *Male Sex
- *Height
- *Weight
- Post-resuscitation chest pain

- Charlson Comorbidity
- Age Adjusted for Charlson Comorbidity Index (CCI)
- *New York Heart Association (NYHA) class pre-OHCA (if no surrogate is present and no medical records are found on the subject this will be assumed to be NYHA class I)
- Barthel ADL pre-OHCA
- Education level
- Private insurance
- Medicare
- Medicaid
- Employed
- Active smoker
- Smoker >20 pack-years
- Prior stroke
- Prior Coronary artery bypass grafting (CABG)
- Noninsulin-dependent diabetes mellitus (NIDDM2) type 2
- Insulin-dependent diabetes mellitus (IDDM2) type 2
- Diabetes mellitus (DM1) type 1
- Prior myocardial infarction (MI)
- Congestive Heart Failure (CHF)
- Chronic Obstructive Pulmonary Disease (COPD)
- Prior cardiac arrest
- Dementia
- Hyperlipidemia
- Hypertension
- Prior coronary stent
- Obstructive sleep apnea
- Pulmonary hypertension
- *Location pre-OHCA

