2.3.3. Dose Selection

A number of studies have reviewed the safety of iNO in adults primarily in the setting of acute respiratory distress syndrome (ARDS). A recent meta-analysis found improved oxygenation but also greater acute kidney injury (AKI) resulting from iNO use.²⁵ When this was examined by dose, AKI only resulted in those patients receiving higher cumulative doses of iNO (≥ 40 ppm for ≥ 48 h).²⁶ Our study will limit iNO to 20 ppm for 12h hence AKI is not expected though we will track BUN and creatinine on all subjects. A separate meta-analysis examining effects of iNO in

acute hypoxic respiratory failure in adults and children found no associated adverse events.²⁷ A study of iNO used in transport identified no adverse events associated with the drug.²⁸ Although iNO significantly increases methemoglobin (metHb) levels, the increase (0.3%) is clinically insignificant and not associated with toxicity²⁹ which is uncommon until levels of 20-30% (we will consider > 10% a significant and unexpected adverse event). The best predictor of significant metHb >4% (as < 0-3% is considered within normal range) is cumulative iNO dose of >2000 ppm * h.³⁰ In our study subjects will receive only 250 ppm * h. We will monitor methemoglobin as part of our study at 6h. Although iNO lowers pulmonary blood pressure it has not been linked to reduction in systemic arterial blood pressure. We will monitor blood pressure effects closely in our study given the inherent instability of cardiac arrest subjects.

Effects of iNO after cardiac arrest has been studied in 4 preclinical animal studies.⁸⁻¹¹ These published studies demonstrated benefit using iNO 40 ppm started within 2h of ROSC which is additive to therapeutic hypothermia⁸ as well as neuroprotection without temperature control.⁹ These animal models include mouse and pig models of asystole and ventricular fibrillation (VF). In addition iNO has been shown to protect in animal models of focal heart¹²⁻¹⁵ and brain¹⁶⁻¹⁹ injury. This is important since most of the mortality and morbidity after OHCA results from heart and brain injury.²⁰

Animal models of asphyxia²¹ and other focal brain ischemia reperfusion models demonstrate NO deficiency early in reperfusion lasting at least 6h and benefits from iNO.^{16,19}

Information from prior clinical trials of iNO are available by cross reference in the Mallinckrodt NDA 20-845 (letter authorizing cross reference is included with application).

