6. POTENTIAL RISKS AND BENEFITS

6.1 POTENTIAL RISKS

6.1.1 Risk of Experimental Drug Intervention

The known adverse events due to iNO are reviewed in the package insert and in section 2.3.3 above. Extensive safety data is available from published studies of iNO in critically ill patients with up to 2 year follow up.¹⁻⁶ In these studies rare cases of MetHb or excess nitrogen dioxide [NO₂], an airway irritant, are reported. These cases occur at doses ≥ 40 ppm. The INOVent delivery system provides constant monitoring of NO₂ levels and we will monitor MetHb to avoid toxicity. iNO may cause rebound hypoxia after prolonged use but this generally requires over 24h of use. We plan a 1h wean off the study drug to minimize this risk. Other NO donors (not iNO) can reduce blood pressure but this has not been noted in human or animal studies of iNO at the doses we plan to use. Acute kidney injury (AKI) has been noted in some clinical trials of iNO but again only with higher doses than we propose to use. We will nonetheless monitor BUN and creatinine as markers of renal function. Patients receiving iNO may experience increasing capillary wedge pressure and worsening heart failure. We will monitor oxygen requirement (FiO₂) and saturation (SpO₂) hourly during study drug administration and the PI or a physician coI will be notified of an increase of $>20\%$ in the patients' oxygen delivery (mechanical ventilator FiO₂) or a drop of > 50 mm Hg or 25% reduction (whichever is lesser) in the PaO₂ if the patient is on FiO₂ > 0.80 . This data along with any change in chest X ray (generally obtained daily in these patients) and hemodynamics collected hourly and hourly fluid intake and output will also be reviewed for each patient by the safety monitor as described above (2.3.5).

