6.4.2 Data Safety Monitoring Plan

Data Monitoring Plan. The proposed study will use the FDA definition of adverse events (AE) and serious adverse events (SAE). Any SAE, which is unexpected and related to study intervention, will be reported immediately to the IRB and will be followed by an additional letter detailing the nature of the SAE. In the event that a participant either withdraws from the study or the investigators decide to discontinue a participant due to a SAE, the participant will be monitored by the co-PIs until (a) a resolution is reached (e.g., the problem has resolved or stabilized with no further change expected), (b) the SAE is determined to be clearly unrelated to the study intervention, or (c) the SAE results in death. Outcomes of SAEs will be regularly reported to the IRB and the sponsor. A summary of the SAEs that occurred during the previous year will be included in the annual progress report as well as in the annual IRB renewal.

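### Section 6.4.7 ends lab and imaging data for subjects withdrawn over a suspected SAE, exempts no safety labs, and conflicts with 2.2, 6.4.2 and itself: a minor safety-data issue

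*Combined protocol and SAP*

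**What the plan says.** Section 6.4.7 deals with two kinds of withdrawal in one paragraph.

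- Subjects withdrawn "due to concern for SAE will be followed for all clinical outcomes but no further lab or imaging data will be collected".
- The paragraph then says: "Subjects will not be withdrawn after enrollment except if requested by the subject or surrogate after notification". For these requested withdrawals, the data and specimens "obtained up to that time and clinical outcomes to DC will be retained".

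Other sections bear on the same subjects.

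- Section 6.4.2 foresees that "the investigators decide to discontinue a participant due to a SAE". It then requires that "the participant will be monitored by the co-PIs until (a) a resolution is reached", or until the event is judged clearly unrelated or ends in death. It names no labs.
- Section 2.2 stars certain elements as essential and says of them: "These data elements should be obtained in all subjects with no missing data expected". The starred elements include methemoglobin (at 6 h only), troponin, blood gas and lactate during dosing, and the daily highest BUN and creatinine on days 1 to 3.
- Section 2.3.3 says of kidney injury: "hence AKI is not expected though we will track BUN and creatinine on all subjects". Section 6.1.1 repeats the commitment: "We will nonetheless monitor BUN and creatinine as markers of renal function".
- Sections 2.3.6 and 6.5.2 allow study drug to be stopped for safety. Neither says that stopping drug is withdrawal from the study.

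**The concern.** The rule in 6.4.7 ends lab collection because harm is suspected, in the subjects whose later safety values are of most interest. It exempts none of the labs that 2.2 calls essential.

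The paragraph is also inconsistent. It treats SAE withdrawals as a group with its own follow-up rule, then says that only requested withdrawals occur. A coordinator with such a subject could not follow 6.4.7, 6.4.2 and 2.2 together.

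What is at stake is safety data. Several SAE definitions in 6.4.5 have a laboratory limb (creatinine above 2.3 mg/dL, raised lactate, base deficit). A SUAE is defined there by methemoglobin above 10%, and methemoglobin has one scheduled draw. Section 2.5.4 compares the listed safety outcomes with exact tests. Section 2.5.5 assumes missing at random without imputation, though it allows sensitivity analyses.

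**Working it through.** The plan gives no figure to reproduce on this point, and no count of such withdrawals. The check is how many starred post-baseline values one withdrawn subject would lose. The 0 h values are already in hand.

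**Inputs**

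- Drug starts within 4 h of ROSC, runs 12 h and is weaned over 1 h (2.1).
- Day 1 is the first 24 h after ROSC (2.2).
- Methemoglobin: one draw, at 6 h (2.2, Table 1).
- Troponin, blood gas and lactate: Table 1 has both 6 h and 12 h; the starred line in 2.2 can be read as requiring one or both.
- BUN and creatinine: one highest value per day, days 1 to 3 (2.2). They are not in Table 1 and may be collected retrospectively.

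**Timing.** The latest end of dosing and wean is 4 + 12 + 1 = 17 h after ROSC. This is under 24 h, so a withdrawal during dosing falls in day 1. The day-2 and day-3 BUN and creatinine are then still to come: 2 labs × 2 days = 4 values.

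**Dosing labs.** Methemoglobin gives 1 value. The other three labs give 3 × 1 = 3 values if one time suffices, or 3 × 2 = 6 if both are required.

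| Withdrawn | Dosing labs lost, either reading | With BUN and creatinine, literal reading |
|---|---|---|
| Before 6 h | 1 + 3 = 4 to 1 + 6 = 7 | 4 + 4 = 8 to 7 + 4 = 11 |
| 6 to 12 h | 0 to 3 | 0 + 4 = 4 to 3 + 4 = 7 |
| After 12 h, day 1 | 0 | 4 |
| Day 2 | 0 | 2 (day 3 only) |

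The counts assume that the subject survives to each time point; 6.4.5 expects 70-80% mortality. They leave out plasma nitrite, which is starred but mechanistic (1 to 2 more before 6 h, 0 to 1 from 6 to 12 h). They also leave out the 24 h blood gas, lactate and troponin peak in 2.4, and any shortening of the day-1 BUN and creatinine maximum.

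**Which reading of lab data?** The visit table in 2.2 lists labs and clinical lab data as separate items on days 1 to 3, and ECHO and LSCI are marked as research procedures. So 6.4.7 may mean study draws and study imaging only. Chart BUN and creatinine would then continue and the conflict with 2.3.3 would disappear. Section 6.4.7 does not say which is meant. The scheduled dosing labs are lost either way.

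**How likely is a missed high methemoglobin?** Exposure before 6 h is at most 20 ppm × 6 h = 120 ppm·h. Section 2.3.3 gives more than 2000 ppm·h as the best predictor of a level above 4%. The ratio is 120 / 2000 = 6%, so a level above 10% in that window is unlikely on the protocol's own figures.

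**The case against.** The strongest reply is that the group may be empty. Section 6.4.7 itself bars withdrawal except on request, 2.3.6 calls a safety stop unanticipated, and 6.5.2 lets investigators stop drug without withdrawing anyone. This largely stands: the number is very small and could be zero. It does not remove the point, because 6.4.2 expressly provides for investigators discontinuing a participant over an SAE, and 6.4.7 writes a rule for that group. If the group is meant to be empty, the rule should go.

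A second reply is that ending research draws after suspected harm is defensible in subjects enrolled under exception from consent. That holds for mechanistic samples, ECHO and LSCI. It is weaker for the few labs that the protocol itself marks as essential to the study and its efficacy or safety analysis.

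Three stronger readings are tempting, and the documents do not support them.

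- **That renal follow-up is certainly lost.** BUN and creatinine may be chart data outside the rule, as shown above.
- **That a SUAE would be missed.** The exposure figures make this unlikely. The safety monitor can also unblind on clinical judgement (2.3.5), and 6.4.6 recognises a SUAE found through unblinding. Merely keeping the 6 h draw would not settle the matter either: after an early drug stop, it does not show the level at the time of the event.
- **That the SAE comparison is biased by a known amount.** With 130 / 2 = 65 per arm, one uncaptured event would move an arm's rate by 1/65 = 1.5 points, but nothing gives a count of such events. Baseline lactate and blood gas, the urine-output limb, discharge-summary events and 6.4.2 monitoring all recover part of the information. Missingness that follows a recorded SAE is also not automatically outside missing at random.

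**Conclusion.** The point holds as a minor safety-data issue. Section 6.4.7 stops lab and imaging collection after an SAE-related withdrawal with no safety exception. It conflicts with 2.2, with 6.4.2 and with its own next sentence and, on the literal reading only, with 2.3.3.

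For each affected subject, the loss on either reading is 4 to 7 scheduled starred values if withdrawn before 6 h and 0 to 3 from 6 to 12 h. The literal reading adds 4 for a day-1 withdrawal, or 2 in total for a day-2 withdrawal. These counts rest on survival to each time point and on whether one or both dosing times are required.

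A reader might infer a threat to the main result. There is none: clinical outcomes are still followed, so the primary composite, the sample size and its power are untouched. No change in any safety test is shown.

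**What to change.** Rewrite the first paragraph of 6.4.7 to say the following.

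- A subject whose drug is stopped, or who is discontinued for a suspected SAE, stays in the study for safety follow-up unless the subject or surrogate refuses.
- If drug is stopped for an SAE before the 6 h sample, methemoglobin is drawn at the time of stopping.
- The remaining scheduled blood gas, lactate and troponin continue.
- BUN and creatinine for days 1 to 3, and clinical imaging, are abstracted from the chart.
- Research-only ECHO, LSCI and mechanistic draws may stop.

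Align the paragraph with 6.4.2, and remove the clash between the SAE rule and the sentence limiting withdrawal to requests.

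The cost is one paragraph of protocol text and some chart abstraction. The downside is a few small draws in unstable subjects enrolled under exception from consent; under 6.1.2 they come from catheters already in place.

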6.5 RISKS MANAGEMENT PROCEDURES

6.5.1 Protection Against Risks

General Risks of Study Protocol and Procedures

All research interventions/activities will be conducted in private patient care areas. The collection of sensitive information about subjects is limited to the amount necessary to achieve the aims of the research, so that no unneeded sensitive information is being collected. Specifically we will only obtain 4 elements of protected health information (PHI) which could identify the subjects. These elements are the subject name (first, middle initial, last), date of birth and UPMC medical record number. These data elements will be stored in a password protected Microsoft Excel spreadsheet which links the PHI to the subject identifier (ID). The document will be stored on a UPMC cloud server drive accessible only to the principal investigator (PI) and data manager. This folder lies behind the UPMC firewall and hence has all security provisions attributable to the electronic medical record associated with it.

Those data elements which will be obtained by direct observation or physical examination of subjects will initially be recorded on a Case Report Form (CRF) which will be linked to the subject using the subject ID only. The Investigator will review, approve and sign/date each completed CRF; the Investigator's signature serving as attestation of the Investigator's responsibility for ensuring that all clinical and laboratory data entered on the CRF are complete, accurate and authentic. These data elements will subsequently be transferred by a research assistant to the

electronic database described below. The completed CRF will be stored in a locked filing cabinet within the locked office of the PI.

All staff will sign confidentiality statements. Access to the database will be limited to the data manager and staff under the supervision of the Investigator.

Specimens will be only be referenced by subject ID as described above. These specimens will be stored safely in the custody of the Investigator responsible for the individual assays. The Investigators will limit future access to any remaining sample to only those investigators with prior IRB approval for their studies.

All staff involved in this study are properly credentialed and instructed in the areas of testing, confidentiality, and safety.

The Investigator will retain the data for the entire period of this study and will retain the specified records and reports for up to two years after the marketing application is approved for the investigational drug; or, if a marketing application is not submitted or approved for the investigational drug, until two years after investigations under the IND have been discontinued and the FDA so notified. The Investigator may continue to use and disclose subjects' de-identified information for the purpose of this study for a minimum of seven years after final reporting or publication of the study. If the subject and/or legal representative decide to withdraw or be withdrawn from study participation, they may request that the study data and samples be destroyed. Subject names or other directly identifiable information will not appear on any reports, publications, or other disclosures of clinical study outcomes.

6.5.2 Protection Against Potential Risks of Experimental Intervention

The study drug (iNO) and administration system (INOVent) are already in clinical use within the UPMC system in the ICUs where subjects will receive care. Existing protocols for administration will be followed by trained RTs. The investigators are all qualified to perform the elements of data acquisition whether by exam, observation or phlebotomy as described below (8.1). All members of the study team will have received required training on protection of human research participants (CITI Good Clinical Practice Module) and all have prior clinical trial experience. During study drug administration the patient's VS, need for vasopressor/inotropic medications, ventilator settings, fluid balance and labs will be reviewed by a research assistant present throughout administration who will report any adverse events to a physician member of the PCAS team (on call 24/7). The PCAS co-investigators are empowered to stop study drug based on their discretion as is the safety monitor who can be consulted if needed. The safety monitor will review data on VS, need for vasopressor/inotropic medications, ventilator settings, fluid balance and labs at least every 4 weeks and data reviewed at least every 6 months by the DSMB.

7. COSTS AND PAYMENTS

7.1 COSTS

No additional cost to patients or insurers for study drug or labs and data collected as part of this study.

7.2 PAYMENTS

No compensation for study participation.

8.2 SOURCES OF SUPPORT

Investigator initiated research award from Mallinckrodt Pharmaceuticals.

